10.6 Additional Safeguards for Vulnerable Subjects

The present research will involve subjects who might be vulnerable to coercion or undue influence. As required in 45CFR46.111(b), we recommend that additional safeguards be included to protect the rights and welfare of these subjects. Such safeguards might include, but are not limited to: a) assessment of the potential subject's capacity to provide informed consent, b) requirement for subject's assent, c) the availability of the LAR to monitor the subject's subsequent participation and withdrawal from the study; d) augmented consent processes. The specific nature of the additional safeguards will be left to the discretion of the individual IRBs.

Minors (13-18 years old)

This study will enroll minors between the ages of 13-18. As this is a vulnerable population the consent form will include a section for obtaining assent for the minor coupled with permission from a parent for both study enrollment and continuation. The assent for continuation will be invoked when surrogate consent is obtained initially (subject not able to self enroll due to illness). In accordance to the decision matrix provided in 45 CFR 46, Children as subjects of research (http://www.hhs.gov/ohrp/panels/407-01pnl/riskcat.htm) we have designed the IRB approved project assent form to require one parental permission signature, as the study is greater than minimal risk with the potential for direct benefit to the subject (46.405).

10.7 Confidentiality

Federal regulations at 45 CFR 46 111 (a) (7) requires that when appropriate, there are adequate provisions to protect the privacy of subjects and to maintain the confidentiality of data. To maintain confidentiality, all laboratory specimens, evaluation forms, and reports will be identified only by a coded number. The coded number will be generated at random by a computer, and only the study investigators will have access to the codes. All records will be kept in a locked, password protected computer. All computer entry and networking programs will be done with coded numbers only. All paper case report forms will be maintained in a locked cabinet inside a locked office. Clinical information will not be released without the written permission of the patient, except as necessary for monitoring by the National Heart, Lung, and Blood Institute, and the ARDS Clinical Coordinating Center.

11 Adverse Event Reporting

Investigators will determine daily if any clinical adverse experiences occur during the period from enrollment through study day 23 or ICU discharge, whichever occurs first. The investigator will evaluate any changes in laboratory values and physical signs and will determine if the change is clinically important and different from what is expected in the course of treatment of patients with ALI or ARDS.

For this trial, a reportable adverse event is defined as:

- 1. Any clinically important untoward medical occurrence in a patient receiving study solution or undergoing study procedures which is different from what is expected in the clinical course of a patient with ALI, or:
- 2. Any clinically important, untoward medical occurrence that is thought to be associated with any component of the study solution (i.e. omega-3 fatty acids, gamma-linolenic acid, or anti-oxidants), or nutritional procedures, regardless of the "expectedness" of the event for the course of a patient with ALI.
- 3. The following protocol specified adverse events should always be reported as adverse events:
 - a. Hypersensitivity to enteral feeds
 - b. Intestinal ischemia or infarction

The investigator will evaluate any changes in laboratory values and physical signs and will determine if the change is clinically important and different from what is expected in the clinical course patients with ALI. *Expected events for ALI* are untoward clinical occurrences that are perceived by the investigator to occur with reasonable frequency in the day to day care of patients with ALI treated in an intensive care unit with mechanical ventilation. Examples of adverse events that are expected in the course of ALI include transient hypoxemia, agitation, delirium, nosocomial infections, intolerance of gastric feeding, skin breakdown, and gastrointestinal bleeding. Such events, which are often the focus of prevention efforts as part of usual ICU care, will not be considered reportable adverse events unless the event is considered by the investigator to be associated with the study drug or procedures, or unexpectedly severe or frequent for an individual patient with ALI. Examples of unexpectedly frequent adverse events would be repeated episodes of unexplained hypoxemia, in contrast to an isolated episode of transient hypoxemia (eg. Sp02 ~85%), particularly if related to positioning of suctioning. This latter event would not be considered unexpected by nature, severity or frequency.

11.1 Clinical Outcomes

Events leading to death and organ failure are being systematically captured in the case report forms and will be systematically analyzed per protocol as part of the safety and efficacy analysis. The following clinical outcomes will not be considered to be adverse events *if the investigator determines the outcomes were not study solution or procedure-related:*

- 1 Death
- 2. Respiratory: worsening hypoxia, prolonged need for ventilation, hypoxemia, hypercarbia, respiratory acidosis, high airway pressures.
- 3. Circulatory: circulatory shock requiring vasopressors.
- 4. Hepatic: hepatic injury that leads to a rising bilirubin.
- 5. Renal: rising creatinine.
- 6. Coagulopathy: falling platelet count.

In addition, patients with acute lung injury who receive enteral nutrition often experience gastrointestinal intolerances (see Section 5.1.7). These gastrointestinal intolerances, including diarrhea, vomiting, constipation, nausea, and abdominal distention will be systematically collected and analyzed as part of the protocol. As such, they will not be considered to be adverse

events. Similarly, patients with acute lung injury also often have elevated gastric residual volumes, which are also being systematically collected and analyzed as part of the protocol and will not be considered an adverse event.

An event will be considered to be study-related if the event follows a reasonable temporal sequence from the study drug/procedure and could readily have been produced by the study drug/procedure. An event will be considered to be *unexpected for study drug* if it is not identified in the study protocol.

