5.1.7.2 Aspiration

Aspiration is defined as the presence of food in the lungs. This will be determined by the primary medical team, but will include visualization of enteral feeds in the endotracheal tube or enteral formula suctioned from the endotracheal tube.

When aspiration occurs, the tube will be checked to confirm that it terminates in the correct location (gastric or post-pyloric). The manner in which the tube position is confirmed will be determined by the primary medical team, but will include either auscultation of air forced through the tube or obtaining a radiographic study. If the feeding tube terminates in the esophagus, it should be repositioned and tube feeds restarted at 25 cc / hr less than the previous rate (minimum of 10 cc / hr) for the full-calorie feeding group and 20 kcal / hr for the trophic feeding group. If the feeding tube terminates distal to the esophagus, enteral feeds will be held for 6 hours. After 6 hours, enteral feeds will be restarted at 25 cc / hr less than the previous rate (minimum of 10 cc / hr) for the full-calorie feeding group and 20 kcal / hr for the trophic feeding group.

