Serum magnesium and phosphorus	Х	Х	Α	Х	Α	Α	Α	Α	Х	Α	Α	Α	Α				
Total Protein and Albumin	Х	Х	Α	Α	Α	Α	Α	Х	Α	Α	Α	Α	Х				
Ventilator–Associated Pneumonia assessment ^v	Α	Α	Α	Α	Α	Α	Α	Α	Α	Α	Α	Α	Α	Α	Α	Α	
Insulin dose at time of glucose level	Α	Α	Α	Α	Α	Α	Α	Α	Α	Α	Α	Α	Α				
Location of Feeding tube (e.g., gastric, post-pyloric) *	Х	Α	Α	Α	Α	Α	Α	Α	Α	Α	Α	Α	Α				
Volume of tube feeds / Calories delivered *		Х	Х	Х	Х	Х	Х	Х	Х	Х	Х	Х	Х				
Number and type of Gastrointestinal Intolerances		Х	Х	Х	Х	Х	Х	Х	Х	Х	Х	Х	Х				
Pro-kinetic agents, anti-diarrheals, anti-emetics * (Y/N)	Х	Х	Х	Х	Х	Х	Х	Х	Х	Х	Х	Х	Х				
Prothrombin Time	Α	Α	Α	Α	Α	Α	Α	Α	Α	Α	Α	Α	Α				
Plasma for Cytokines IL-6 and IL-8	Х			Х			Х						Х				
Urine isoprostane metabolites	Х			Х			Х										
Whole blood for DNA	Х																
Episode of bacteremia (record positive blood cultures) *		Α	Α	Α	Α	Α	Α	Α	Α	Α	Α	Α	Α	Α			
Clostridium dificile diarrhea tests		Α	Α	Α	Α	Α	Α	Α	Α	Α	Α	Α	Α	Α			
Vital Status §																Х	Х

A=When available

 $^{^{\}text{C}}=$ Labs not available in the 24 hours before randomization must be obtained

V = VAP assessment from available CXR, sputum culture, gram stain and WBC until extubated or day 28, whichever occurs first *= Data gathered at times indicated or until 48 hours UAB, whichever occurs first **=On day 28 or hospital discharge dates.

B=Records clinically available creatinine, platelets, bilirubin, SBP and vasopressor use

^{~=}Data gathered on days 0-28 or until d/c from study hospital

^{#=}Measure during reference period (0600-1000); other values may be obtained closest to 0800 on the specified calendar date §=Measure at 90 days and 12 months as part of Long Term outcome.

F Adverse Events

1. Procedures for Reporting Adverse Events

Assuring patient safety is an essential component of this protocol. Each participating investigator has primary responsibility for the safety of the individual participants under his or her care. The Principal Investigator will evaluate all adverse events. The Study Coordinator must view patient records for possible adverse events throughout the study period. All adverse events occurring within the study period must be reported in the participants' case report forms.

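### Section 11.1 exempts gastrointestinal intolerances (by reference including aspiration) and elevated gastric residuals from adverse-event status without condition, while Section 11 keeps the clinically important, feeding-related ones reportable

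*Protocol*

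**What the plan says.** **Section 11 (Adverse Event Reporting).** Item 2 of the definition covers clinically important untoward occurrences thought to be associated with the study solution "or nutritional procedures, regardless of the" expectedness of the event. The paragraph on expected events lists intolerance of gastric feeding among its examples and says that such events "will not be considered reportable adverse events unless the event is considered by the investigator to be associated with the study drug or procedures", or are unexpectedly severe or frequent for the individual patient. Investigators assess adverse events through study day 23 or ICU discharge, whichever is first. Two events must always be reported: hypersensitivity to feeds, and intestinal ischemia or infarction.

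**Section 11.1 (Clinical Outcomes).** Death and a list of organ-level outcomes are not adverse events "if the investigator determines the outcomes were not study solution or procedure-related". The next paragraph turns to feeding: "In addition, patients with acute lung injury who receive enteral nutrition often experience gastrointestinal intolerances (see Section 5.1.7"). It continues: "These gastrointestinal intolerances, including diarrhea, vomiting, constipation, nausea, and abdominal distention will be systematically collected and analyzed as part of the protocol", and then "As such, they will not be considered to be adverse" events. Elevated gastric residual volumes get the same exemption.

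**Section 5.1.7.** Aspiration is one of the gastrointestinal intolerances set out here; 5.1.7.2 reads "Aspiration is defined as the presence of food in the lungs". Sections 2.4 and 3.3 also list aspiration as a gastrointestinal intolerance.

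**Section 11.2 and Appendix F.** Reporting within 24 hours applies to adverse events that are serious, unexpected and study-related. Appendix F treats an event as unexpected if its type, severity or frequency is not identified in the protocol. It repeats the conditional exemption for organ failures and has none for intolerances.

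**Appendix E.** The row "Number and type of Gastrointestinal Intolerances" is marked on days 1 to 12.

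**The concern.** Two rules in one chapter classify the same event in opposite ways. The exemption for death and organ failure depends on the investigator judging the outcome unrelated to the study. The exemption for feeding intolerances, which are the events most directly tied to the intervention, has no such condition.

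The protocol itself expects these events to differ between arms. Section 9.2 says that early full-calorie feeding could lead to more vomiting and aspiration, and the primary hypothesis in Section 2.3 works partly through fewer feeding complications. Section 11.2 has the DSMB review all adverse events at its interim analyses. The safety parameters in the Study Summary name adverse-event reporting but not intolerances. If a related, clinically important aspiration is not an adverse event, it does not reach the DSMB by that route.

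**Working it through.** The only arithmetic is a day count; the rest is a comparison of rules.

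**Step 1. Is aspiration inside the exempt class?** Section 11.1 does not name it. The class is set by the reference to Section 5.1.7, and the list of examples is open (it begins with the word including). Section 5.1.7 introduces its subsections as gastrointestinal intolerances, and 5.1.7.2 is aspiration. Sections 2.4 and 3.3 agree. Aspiration is not on the always-report list. The natural reading is that it is exempt, although 11.1 never says so.

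**Step 2. Apply each rule to the same events.**

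| Event | Section 11 | Section 11.1 |
|---|---|---|
| Routine intolerance, not clinically important, of expected severity and frequency | Not reportable | Not an adverse event |
| Clinically important intolerance judged related to study feeding | Reportable (item 2) | Not an adverse event |
| Intolerance unexpectedly severe or frequent for that patient | Reportable (expected-events paragraph) | Not an adverse event |
| Hypoxemia or death judged procedure-related | Reportable | Still an adverse event (condition not met) |

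The rules agree on rows 1 and 4 and conflict on rows 2 and 3.

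**Step 3. Which of these events touch the 24-hour route?** The route needs an adverse event that is also serious, unexpected and study-related. Vomiting and aspiration are identified as risks in Section 9.1, so an ordinary episode is not unexpected in type. Under Appendix F an episode can still be unexpected in severity or frequency. Only that subset, when also serious and related, qualifies under Section 11 and Appendix F and is lost under 11.1. The other conflicting events lose ordinary adverse-event reporting only.

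**Step 4. For how long could an event be missed by both routes?**
- Days on which study feeding can continue: to day 28, or until extubation or 48 hours of unassisted breathing (Section 5.1.8).
- Intolerance recording in Appendix E: days 1-12.
- Adverse-event assessment in Section 11: through day 23 or ICU discharge.
- Days after intolerance recording stops: 28 − 12 = 16.
- Of these, days outside the adverse-event window whatever 11.1 says: 28 − 23 = 5 (days 24-28).
- Days on which 11.1 makes the difference: 16 − 5 = 11 (days 13-23). This is an upper limit, since ICU discharge or the end of study feeding shortens it.

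On days 1-12 the number and type of intolerances are scheduled for recording, so what is lost is the adverse-event report and not the record of the event.

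**The case against.** The exemption has a stated reason: intolerances are collected and analyzed as study data. Section 5.1.7 standardizes the response to them, Section 3.3 makes their number on days 1-7 an endpoint, and pneumonia assessment runs to day 28 while the patient is intubated. The DSMB parameter list is not closed, so intolerance data may reach the board. This reason stands for routine episodes. It does not explain why Section 11 keeps related or unexpectedly severe episodes reportable and 11.1 does not.

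A reader might infer more than the documents support:

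- **That any serious feeding harm escapes 24-hour reporting.** It does not. The route also needs the event to be unexpected, and Section 11.1 itself describes unexpected (for study drug) as not identified in the protocol. Only the severity or frequency clause of Appendix F brings in a subset.
- **That an aspiration followed by arrest would go unreported.** Arrest is on no exemption list. Hypoxemia, shock and death are exempt only if not procedure-related. The consequence stays reportable; the gap is the intolerance itself, including a serious episode without such an outcome.
- **That 16 days are uncovered.** Five of them lie outside the adverse-event window in any case.
- **That seriousness and outcome are not recorded for intolerances.** This would rest on a row label in a schedule. The case report form is not in the documents.
- **That adverse-event counts do differ between sites.** Different readings are possible, but nothing in the documents shows that they occurred.

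It is also fair to object that aspiration enters only by cross-reference, and that the list in 11.1 is not a copy of 5.1.7, since it names nausea, which has no subsection there. That uncertainty is itself a reason to state the status of aspiration.

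**Conclusion.** The contradiction is real and should be resolved. Section 11.1 removes, without condition, events that Section 11 item 2 and the expected-events paragraph require to be reported: clinically important intolerances related to study feeding, and those of unexpected severity or frequency. Appendix F offers no support for the unconditional wording.

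The reach is limited. Ordinary adverse-event reporting is affected for the whole of that group. The 24-hour route is affected only for the part that is serious, study-related and unexpected in severity or frequency. Loss by both routes is confined to days 13-23, at most 11 days per patient. Minor intolerances were never reportable, and procedure-related downstream outcomes remain so.

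This rests on two readings: that the reference to Section 5.1.7 brings aspiration into the exempt class, and that the Appendix E row gives the full period of intolerance recording. The number of events concerned cannot be estimated from the protocol.

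**What to change.** Reconcile Sections 11 and 11.1 with one sentence in 11.1, to this effect: gastrointestinal intolerances and elevated gastric residual volumes are not adverse events unless they are clinically important and judged related to study feeding procedures, or are unexpectedly severe or frequent for the individual patient; an aspiration (5.1.7.2) that is clinically important and related to study feeding is reportable under Section 11 item 2.

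These are Section 11's own conditions, so no new standard is introduced. The clinically important threshold must be kept: a relatedness condition alone could turn routine diarrhea or a raised residual into an adverse event in a trial where every patient is tube-fed.

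The cost is the sentence, a memo to sites and a modest number of extra adverse-event reports. Those reports will rest on relatedness judgments in a trial where feeding volumes are unblinded, but Section 11 already relies on such judgments. Routine intolerances stay exempt and continue to be collected as study data.

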11.2 Adverse Event Reporting Timeline

Investigators will report all serious, and unexpected, and study-related adverse events, as defined in Appendix F, to the Clinical Coordinating Center by telephone, fax, or email within 24 hours. The local Institutional Review Board must also be notified in a timely manner. The investigator will then submit a detailed written report to the Clinical Coordinating Center and the Institutional Review Board no later than 5 days after the investigator discovers the event.

The Clinical Coordinating Center will report all serious, unexpected, and study-related adverse events to the NHLBI within 24 hours. A written report will be sent to the DSMB within 15 calendar days and these reports will be sent to investigators for submission to their respective Institutional Review Boards. The DSMB will also review all adverse events during scheduled interim analyses. The Clinical Coordinating Center will distribute the written summary of the DSMB's periodic review of adverse events to investigators for submission to their respective Institutional Review Boards in accordance with NIH guidelines.

APPENDICES

A Identification of Ventilator-Associated Pneumonia

Suspected or Possible Pneumonia: patient must meet at least one criterion from two categories below (i, ii or iii).

Probable Pneumonia: patient must meet at least one criterion from all three categories below (i and ii and iii).

- i. Chest radiograph shows new infiltrate corresponding in size (although not necessarily to segmental anatomical boundaries) to at least one segment or cavitation with an air-fluid level within an area of infiltrate (*i.e.*, not a simple subpleural air cyst). The qualifying radiographic abnormality must persist over at least 48 hours with no decrease in its size.
- ii. New onset of or increase in fever ($T \ge 38.3^{\circ}C$ or increase $\ge 1^{\circ}C$ over the previous 24 hour T_{max} if T already $\ge 38.3^{\circ}C$) or new hypothermia ($T \le 36.0^{\circ}C$) or increase in WBC (WBC > 10,000 and a 25% increase or an increase in band forms to > 10% of total WBC) or new decrease in WBC to < 4,000.
- iii. Bacteriological confirmation of pulmonary infection (can be any of the following):
 - quantitative culture of tracheal secretions with > 10⁶ cfu/mm³
 - quantitative culture of bronchoalveolar lavage with > 10⁴ cfu/mm³
 - quantitative culture of protected specimen brush with > 10³ cfu/mm³
 - positive Gram stain with $\geq 3+$ of at least one type of bacteria.
 - positive semi-quantitative sputum culture with \geq 3+ growth of at least one type of potentially pathogenic bacteria
 - positive blood culture for bacterial pathogen also identified in sputum or other respiratory specimens
 - positive Gram stain or culture of pleural fluid for bacterial pathogen

Only one episode will be considered to be present during the 28-day period for the following due to difficulty in defining successful therapy during this time period.

B Exclusion Definitions

1. Malignant and Irreversible Conditions

- a. Poorly controlled neoplasms (proven by surgery, computed tomographic scan, biopsy or other documented method)
- b. Known HIV positive with known end stage processes (e.g., progressive multifocal leukoencephalopathy, systemic mycobacterium avium infection) with known CD4 count < 50.
- c. Prior cardiac arrest requiring CPR without fully demonstrated neurologic recovery
- d. New York Heart Association Class IV subjects (defined as subjects who have cardiac disease resulting in inability to carry out physical activity without discomfort. Symptoms of cardiac insufficiency or of anginal syndrome may be present even at rest. If any physical activity is undertaken, discomfort is increased).
- e. Chronic respiratory condition making patient respirator dependent.

2. Refractory Shock

Refractory shock is defined as the requirement of any of the following to obtain a blood pressure adequate for perfusion of tissues

- a. Dopamine infusion at rate $\geq 15 \text{ mcg} / \text{kg} / \text{min}$
- b. Dobutamine infusion at rate $\geq 15 \text{ mcg}/\text{kg}/\text{min}$
- c. Epinephrine or Norepinephrine infusion at rate $\geq 30 \text{ mcg} / \text{min}$
- d. Phenylephrine infusion at rate $\geq 50 \text{ mcg} / \text{min}$
- e. Milrinone infusion at rate $\geq 0.5 \text{ mcg} / \text{kg} / \text{min}$
- f. Vasopressin infusion at rate > 0.04 U / min
- g. Intra-aortic Balloon Pump

3. Child-Pugh Score (Pugh, 1973)

Points	Clas
5-6	A
7-9	В
≥ 10	C

	Numerical Score for Increasing Abnormality						
Measurement	1	2	3				
Ascites	None	Present	Tense				
Encephalopathy	None	Grade I or II	Grade III or IV				
Bilirubin (mg/dl)	< 2	2-3	> 3				
Albumin (g/L)	> 35	28-35	< 28				
Prothrombin time (sec. prolonged)	1-4	4-10	> 10				

4. Neuromuscular Disease Impairing the Ability to Ventilate Spontaneously

[figure not shown]
- a. Amyotrophic lateral sclerosis
- b. Guillain-Barré Syndrome
- c. Myasthenia gravis
- d. Upper spinal cord injury at level C5 or above
- e. Kyphoscoliosis or chest wall deformity resulting in severe exercise restriction (unable to climb stairs or perform household duties), secondary polycythemia, or respirator dependence

5. Severe Chronic Respiratory Disease

[figure not shown]
Any of the following is considered severe chronic respiratory disease and excludes a patient from being eligible for enrollment:

- 1. FEV₁ less than 20 ml/kg PBW (e.g. 1.4 L for a 70 kg person), or
- 2. FEV₁/VC less than 50% predicted, or
- 3. Chronic hypercapnia (PaCO₂ greater than 45 mmHg) and/or chronic hypoxemia (PaO₂ less than 55 mmHg) on $F_1O_2 = 0.21$, or
- 4. Radiographic x-ray evidence of any chronic over-inflation or chronic interstitial infiltration, or
- 5. Hospitalization within the past six months for respiratory failure in patients with chronic respiratory disease. (PaCO₂ greater than 50 mmHg or PaO₂ less than 55 mmHg or O₂-Sat < 88% on FiO₂ = .21).
- 6. Chronic restrictive, obstructive, neuromuscular, chest wall or pulmonary vascular disease resulting in severe exercise restriction, e.g., unable to climb stairs or perform household duties, secondary polycythemia, severe pulmonary hypertension (mean PAP greater than 40 mmHg), or respirator dependency.

C Trophic Feeding Protocol

D Full-calorie Feeding Protocol

Time-Events Schedule \mathbf{E}

Measurement/Event	Day 0	1	2	3	4	5	6	7	8	9	10	11	12	14	21	28	60
Demographics, History & Physical, Height, Weight	X																
Etiology of ARDS, site of sepsis if septic etiology	Х																
APACHE III Score ^C	Х																
HCG (in females)	Х																
Vital Signs (HR, SBP, DBP, Temp °C) *	Х	Х	Х	Х	Х	Х	Х	Х	Х	Х	Х						
Central Venous Pressure *	Α	Α	Α	Α	Α	Α	Α	Α	Α	Α	Α						
Fluids (In and Out) *	Х	Х	Х	Х	Х	Х	Х	Х									
Brussels Score ^B ~	Х	Х	Х	Х	Х	Х	Х	Х	Х	Х	Х	Х	Х	Х	Х	Х	
Glasgow Coma Scale	Х							Х								X**	
Ventilator Parameters (including FiO ₂) *#	Х	Х	Х	Х	Х		Х						Х		Х	Х	
Arterial Blood Gases (PaO ₂ , PaCO ₂ , pH) and SpO ₂	Х	Α	Α	Α	Α		Α						Α		Α	Α	
Serum Glucose, Na+, K+, HCO3-, Hgb	Х	Α	Α	Α	Α	Α	Α	Α	Α	Α	Α	Α	Α				
Creatinine, Platelets, Bilirubin, BUN Hct,	Х																
Chest X-ray (# quadrants for lung injury score)	Α	Α	Α	Α	Α	Α	Α	Α	Α	Α	Α						
Record Sedatives, narcotics, pressors * (Y/N)	Х	Х	Х	Х	Х	Х	Х	Х	Х	Х	Х	Х	Х				
Serum magnesium and phosphorus	Х	Х	Α	Х	Α	Α	Α	Α	Х	Α	Α	Α	Α				
Total Protein and Albumin	Х	Х	Α	Α	Α	Α	Α	Х	Α	Α	Α	Α	Х				
Ventilator–Associated Pneumonia assessment ^v	Α	Α	Α	Α	Α	Α	Α	Α	Α	Α	Α	Α	Α	Α	Α	Α	
Insulin dose at time of glucose level	Α	Α	Α	Α	Α	Α	Α	Α	Α	Α	Α	Α	Α				
Location of Feeding tube (e.g., gastric, post-pyloric) *	Х	Α	Α	Α	Α	Α	Α	Α	Α	Α	Α	Α	Α				
Volume of tube feeds / Calories delivered *		Х	Х	Х	Х	Х	Х	Х	Х	Х	Х	Х	Х				
Number and type of Gastrointestinal Intolerances		Х	Х	Х	Х	Х	Х	Х	Х	Х	Х	Х	Х				
Pro-kinetic agents, anti-diarrheals, anti-emetics * (Y/N)	Х	Х	Х	Х	Х	Х	Х	Х	Х	Х	Х	Х	Х				
Prothrombin Time	Α	Α	Α	Α	Α	Α	Α	Α	Α	Α	Α	Α	Α				
Plasma for Cytokines IL-6 and IL-8	Х			Х			Х						Х				
Urine isoprostane metabolites	Х			Х			Х										
Whole blood for DNA	Х																
Episode of bacteremia (record positive blood cultures) *		Α	Α	Α	Α	Α	Α	Α	Α	Α	Α	Α	Α	Α			
Clostridium dificile diarrhea tests		Α	Α	Α	Α	Α	Α	Α	Α	Α	Α	Α	Α	Α			
Vital Status §																Х	Х

A=When available

 $^{^{\}text{C}}=$ Labs not available in the 24 hours before randomization must be obtained

V = VAP assessment from available CXR, sputum culture, gram stain and WBC until extubated or day 28, whichever occurs first *= Data gathered at times indicated or until 48 hours UAB, whichever occurs first **=On day 28 or hospital discharge dates.

B=Records clinically available creatinine, platelets, bilirubin, SBP and vasopressor use

^{~=}Data gathered on days 0-28 or until d/c from study hospital

^{#=}Measure during reference period (0600-1000); other values may be obtained closest to 0800 on the specified calendar date §=Measure at 90 days and 12 months as part of Long Term outcome.

F Adverse Events

1. Procedures for Reporting Adverse Events

Assuring patient safety is an essential component of this protocol. Each participating investigator has primary responsibility for the safety of the individual participants under his or her care. The Principal Investigator will evaluate all adverse events. The Study Coordinator must view patient records for possible adverse events throughout the study period. All adverse events occurring within the study period must be reported in the participants' case report forms.

Investigators will report all *serious*, *unexpected*, *and study-related* adverse events to the Clinical Coordinating Center by telephone, fax, or email within 24 hours. The local Institutional Review Board must also be notified in a timely manner. The investigator will then submit a detailed written report to the Clinical Coordinating Center and the local Institutional Review Board no later than 5 days after the investigator discovers the event.

2. Definitions of Adverse Events

A *serious* adverse event is any event that is fatal or immediately life threatening, is permanently disabling, or severely incapacitating, or requires or prolongs inpatient hospitalization. Important medical events that may not result in death, be life threatening, or require hospitalization may be considered serious adverse events when, based upon appropriate medical judgment, they may jeopardize the patient or subject and may require medical or surgical intervention to prevent one of the outcomes listed above.

Life-threatening means that the patient was, in the view of the investigator, at immediate risk of death from the reaction as it occurred. This definition does not include a reaction that, had it occurred in a more serious form, might have caused death. Assessment of the cause of the event has no bearing on the assessment of the event's severity.

An *unexpected* event is any experience not identified by the type, severity, or frequency in the current study protocol or an event that is unexpected in the course of treatment for ALI or ARDS.

Adverse events will be considered to be study-related if the event follows a reasonable temporal sequence from a study procedure and could readily have been produced by the study procedure.

Organ failures related to ALI or ARDS or the patient's underlying condition should not be reported as adverse events *if the investigator determines the outcomes were not study solution or procedure-related* since they are systematically captured by the protocol data collection.

The following protocol-specified events should always be reported as adverse events:

- a. Hypersensitivity to enteral feeds
- b. Intestinal ischemia or infarction

G Ventilator Procedures

G.1 Ventilator Management

A modified, simplified version of the ARDS Network lung protective lower tidal volume strategy will be used in this trial. This strategy, which was associated with unprecedented low mortality rates in three previous ARDS Network trials (ARMA, ALVEOLI, and FACTT), will ensure that study subjects receive the beneficial effects of lung protection as part of their participation in this trial (Brower, 2004; The Acute Respiratory Distress Syndrome Network, 2000). ARDS Network personnel have substantial experience in the application of this protocol from the three completed trials noted above.

- 1. Any mode of ventilation capable of delivering the prescribed tidal volume (6ml/kg PBW, +/- 2ml/kg) may be used, provided the V_T target is monitored and adjusted appropriately. During APRV, tidal volume is defined as the sum of the volume that results from the ventilator pressure-release and an estimation of the average spontaneous V_T .
- 2. Tidal Volume (Vt) Goal: 6 ml/kg PBW

Predicted body weight (PBW) is calculated from age, gender, and height (heel to crown) according to the following equations:

```
Males: PBW (kg) = 50 + 2.3 [height (inches) -60]
Females: PBW (kg) = 45.5 + 2.3 [eight (inches) -60]
```

- 3. Measure and record inspiratory plateau pressure (Pplat) according to ICU routine (at least every four hours and after changes in Vt and PEEP recommended)
- 4. If Pplat > 30 cm H₂0, reduce Vt to 5 ml / kg and then to 4 ml / kg PBW if necessary to decrease Pplat to \leq 30 cm H₂0.
- 5. If Vt < 6 ml / kg PBW and Pplat < 25 cm H_20 , raise Vt by 1 ml / kg PBW to a maximum of 6 ml / kg.
- 6. If "severe dyspnea" (more than 3 double breaths per minute or airway pressure remains at or below PEEP level during inspiration), then raise Vt to 7 or 8 ml / kg PBW if Pplat remains below 30 cm H₂0. If Pplat exceeds 30 cm H₂0 with Vt of 7 or 8 ml / kg PBW, then revert to lower Vt and consider more sedation.
- 7. If pH < 7.15, Vt may be raised and Pplat limit suspended (not required).
- 8. Oxygenation target: 55 mmHg < PaO2 < 80 mm Hg or 88% < SpO2 < 95%. When both PaO₂ and SpO₂ are available simultaneously, the PaO₂ criterion will take precedence.
- 9. Minimum PEEP = 5 cm H_20
- 10. Adjust FiO₂ or PEEP upward within 5 minutes of consistent measurements below the oxygenation target range

- 11. Adjust FiO₂ or PEEP downward within 30 minutes of consistent measurements above the oxygenation target range.
- 12. There are no requirements for maintaining a specific PEEP to FiO₂ ratio. The lower PEEP / higher FiO₂ table represents a consensus approach developed by ARDS Network investigators in 1995. The higher PEEP / lower FiO₂ table (ALVEOLI) yielded equivalent results in a randomized trial (Brower, 2004) and would be acceptable and perhaps preferable in patients who appear to respond with substantial increase in arterial oxygenation in the transition from lower to higher PEEP.

Lower ELV/Higher FiO₂ Treatment Group

L.O	20	40	40	70	70	(0	70	70	70	0.0	00	00	00	1.0
FiO ₂	.30	.40	.40	.50	.50	.60	.70	.70	.70	.80	.90	.90	.90	1.0
PEEP	5	5	8	8	10	10	10	12	14	14	14	16	18	18-24

Higher ELV/Lower FiO₂ Study Group

					0					 				
FiO ₂	.30	.30	.30	.30	.30	.40	.40	.50	.50	.5080	.80	.90	1.0	1.0
PEEP	5	8	10	12	14	14	16	16	18	20	22	22	22	24

(Levels of PEEP in these FiO₂ / PEEP scales represent levels set on the ventilator, not levels of total-PEEP, auto-PEEP, or intrinsic-PEEP.)

- 13. No specific rules for respiratory rate, but incremental increase in the RR to maximum set rate of 35 if pH < 7.30.
- 14. No specific rules about I:E. Recommend that duration of Inspiration be ≤ duration of Expiration.
- 15. Bicarbonate is allowed (neither encouraged nor discouraged) if pH < 7.30.

Changes in more than one ventilator setting driven by measurements of PaO₂, pH, and Pplat may be performed simultaneously, if necessary.

G.2 Weaning

G.2.1 Commencement of Weaning

Patients will be assessed for the following weaning readiness criteria each day between 0600 and 1000. If a patient procedure, test, or other extenuating circumstance prevents assessment for these criteria between 0600 and 1000, then the assessment and initiation of subsequent weaning procedures may be delayed for up to six hours.

- (a) At least 12 hours since enrollment in the trial.
- (b) $FiO_2 \le 0.40$ and $PEEP \le 8$ cm H_2O or $FiO_2 \le 0.50$ and PEEP = 5 cm H_2O
- (c) Values of both PEEP and $FiO_2 \le values$ from previous day (comparing Reference Measurement values, section 6.3).
- (d) Not receiving neuromuscular blocking agents and without neuromuscular blockade

- (e) Patient exhibiting inspiratory efforts. If no efforts are evident at baseline, ventilator set rate will be decreased to 50 % of baseline level for up to 5 minutes to detect inspiratory efforts.
- (f) Systolic arterial pressure ≥ 90 mm Hg without vasopressor support (≤ 5 mcg / kg / min dopamine or dobutamine will not be considered a vasopressor).

G.2.2 Spontaneous Breathing Trial Procedure and Assessment for Unassisted Breathing

If criteria a-f above are met, then initiate a trial of up to 120 minutes of spontaneous breathing with $F_1O_2 \le 0.5$ using any of the following approaches:

- 1. Pressure support \leq 5cm H₂O, PEEP \leq 5cm H₂O
- 2. CPAP \leq 5 cm H₂O
- 3. T-piece
- 4. Tracheostomy mask

Monitor for tolerance using the following:

- 1. SpO₂ \geq 90% and / or PaO₂ \geq 60 mmHg
- 2. Mean spontaneous tidal volume $\geq 4 \text{ ml / kg PBW (if measured)}$
- 3. Respiratory Rate $\leq 35 / \min$
- 4. $pH \ge 7.30$ (if measured)
- 5. No respiratory distress (defined as 2 or more of the following):
 - a. Heart rate $\geq 120\%$ of the 0600 rate (≤ 5 min at $\geq 120\%$ may be tolerated)
 - b. Marked use of accessory muscles
 - c. Abdominal paradox
 - d. Diaphoresis
 - e. Marked subjective dyspnea.

If any of the goals 1-5 are not met, revert to previous ventilator settings or to PS + 10 cm H_2O with Positive End-expiratory Pressure and FiO_2 = previous settings and reassess for weaning the next morning.

The clinical team may decide to change mode of support during spontaneous breathing (PS = 5, CPAP, tracheostomy mask, or T-piece) at any time.

G.2.3 Decision to remove ventilatory support

For intubated patients, if tolerance criteria for spontaneous breathing trial (1-5 above) are

met for at least 30 minutes, the clinical team may decide to extubate. However, the spontaneous breathing trial can continue for up to 120 minutes if tolerance remains in question. If any of criteria 1-5 are not met during unassisted breathing (or 120 minutes has passed without clear tolerance), then the ventilator settings that were in use before the attempt to wean will be restored and the patient will be reassessed for weaning (see section G.2.1) the following day.

G.3 Definition of Unassisted Breathing

- (a) Extubated with face mask, nasal prong oxygen, or room air, OR
- (b) T-tube breathing, OR
- (c) Tracheostomy mask breathing, OR
- (d) CPAP \leq 5 without PS or IMV assistance

G.4 Completion of Ventilator Procedures

Patients will be considered to have completed the study ventilator procedures if any of the following conditions occur:

- a. Death
- b. Hospital discharge
- c. Alive 28 days after enrollment

